Primary Objectives: Assess the relative effectiveness of the ABC intervention combined with Head Start (HS)-level asthma education (ABC group) in improving asthma morbidity compared to HS-level asthma education alone (Control group) in preschool children with symptomatic asthma. Primary Hypothesis (#1): Participants receiving the ABC intervention will have more symptom free days at the 6-, 9-, and 12-month evaluations when compared with participants in the control group. (#2): Participants receiving the ABC intervention will have reduced morbidity, including decreased urgent care utilization (hospitalizations/ED visits measured by caregiver report as well as insurance payer data), improved quality of life, improved asthma control, and fewer courses of oral steroids, when compared with participants in the Control group at the 6-, 9-, and 12-month evaluations.

Secondary Objectives: Assess the degree to which HS program-level adoption, implementation and maintenance of asthma education activities (stratified as high implementation vs. low implementation) moderates the impact of child-level treatment assignment (ABC vs. Control) on measures of asthma morbidity, including symptom-free days, urgent care, quality of life, asthma control and oral steroids.

Secondary Hypothesis (#3): Participants receiving the ABC home-based intervention combined with high implementation of HS-level asthma education will have reduced asthma morbidity, including decreased urgent care utilization, improved quality of life, improved asthma control, and fewer courses of oral steroids, when compared with participants receiving the ABC intervention in low implementation of HS-level asthma education, or Control group participants at the 6-, 9-, and 12month evaluations. The secondary outcome measures include other measures of asthma morbidity (i.e., ED visits and hospitalizations, oral steroid bursts, asthma control and caregiver quality of life).

3. Background (briefly describe pre-clinical and clinical data, current experience with procedures, drug or device, and any other relevant information to justify the research)

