This study is designed to evaluate the effectiveness of a home-based asthma education intervention (ABC) with demonstrated efficacy in combination with a Head Start level intervention (ABC + HS) to improve asthma morbidity compared to a Head Start level intervention (HS Only) containing asthma education implemented in the Head Start Programs. The study design is a two group randomized clinical trial (N=406). Participants will be children with symptomatic asthma enrolled in Baltimore City Head Start Program Sites (age 2-6) and their families. Participants will be recruited from Head Start and randomly assigned to ABC combined with HS asthma education or HS asthma education alone. The ABC intervention is home- asthma education intervention that was tailored, based on our prior research and that of others, to reflect known cultural barriers to effective asthma management among low-income minority families, including underutilization of asthma primary care, overestimation of asthma control, perceptions that asthma is an episodic illness that only needs acute treatment, negative beliefs about controller medications, and environmental risk factors in the home. All intervention visits will be audio-taped. Outcome measures will be collected at 3-, 6-, 9- and 12-months. The primary outcome measure will be symptom free days at six month follow-up. Secondary outcome measures include other measures of asthma morbidity (i.e., ED visits and hospitalizations, oral steroid bursts, asthma control, and caregiver quality of life). In addition, at the Head Start level, we will evaluate over five years the overall HS participation in the HS-level asthma education program and any additional programs or institutional changes that would indicate adoption, implementation and maintenance of asthma education as a core HS health goal and changes in HS staff knowledge, attitudes and practices related to asthma management.

Staff Safety

In order to assure safety for our study team we do the following: (1) All of our study team members are provided with a cell phone to be kept with them at all times. (2) We conduct annual safety training with a member of the police department. (3) We request that our study team members not conduct home visits at night. (4) All study team members are encouraged to request a second team member attend any home visit that makes them feel uncomfortable.

Screening

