Asthma Outreach workers: Interested Asthma Outreach Workers will have the study described to them in detail by a JHARC study team member on an individual basis. Asthma Outreach Workers will be told about the study, given an opportunity to ask questions about participation and informed that participation is voluntary and has no effect on their employment status at Johns Hopkins University. Staff participation consists of Asthma training by JHARC staff and a brief knowledge and satisfaction survey pre and post training.

Randomization

Randomization will occur after baseline data collection and the group assignment will be recorded. Children will be individually randomized to either the ABC + HS intervention or HS intervention alone. Blocked randomization will be used so that staff cannot predict which treatment will follow. We will stratify randomization by Head Start program to control for clustering within Head Start programs.

Baseline and Follow-up Assessments

Baseline measures will be collected prior to intervention delivery. The baseline assessment consists of an environmental home assessment, skills checklist, weight and height of the child and a survey, will be completed in the family's home by a research assistant (RA) before randomization. Families who are unable to locate their spacer or state they do not have a spacer, will be provided one at this time. Participants will receive \$50 for completing this home visit.

Follow-up assessments will be completed 3-, 9-, and 12- months and will consist of a survey that will be completed over the phone. Participants will receive \$30 for completing these phone visits. 6-month followup assessments will be conducted in the home and consist of an environmental home assessment, skills checklist, weight and height of the child and a survey. Participants will receive \$50 for completing this home visit.

Current Medication Treatment Plan (CMTP)

A CMTP for each participant will be obtained from the child's asthma care providers at Baseline and 12 month follow-up visits. The CMTP will contain information about start and end dates for asthma medications as well as drug name, dose and prescribed frequency.

Pharmacy Refill History

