Data will be summarized by intervention group (blinded for any interim analyses). Initially we will examine both groups (ABC and Control) for differences in baseline independent/covariate variables (i.e., age, gender, and maternal age). Standard goodness-of-fit tests will be used to determine the approximate normality of the continuous demographic data and response variables under each hypothesis. Data will be transformed as appropriate before hypothesis testing is performed. It is common in prospective studies for a non-trivial fraction of the participants to be lost to follow-up during the course of the study. All outcome analysis will be based upon the intent-to-treat principle (ITT). The sample size calculation and the analytic plan anticipate a 15% loss to follow-up. From a statistical perspective, dropouts can be classified into two major groups: ignorable and non-ignorable. For the former, the probability of dropping out depends upon measured variables, e.g., severity of disease, age and gender. Nonignorable dropouts occur when the probability of dropping out depends upon unobserved quantities, e.g., the outcome that would have been observed had the person not dropped out. We will use statistical methods (weighted Generalized Estimating Equations or likelihood methods) that provide consistent inferences about the intervention effect for ignorable dropout processes. However, all methods of inference can be biased by non-ignorable dropouts. We will conduct sensitivity analyses to determine how extreme the non-ignorable missingness must be to severely compromise the major substantive findings of this research. We will also conduct interclass correlations (ICC) among children recruited from the same HS program for all outcome variables to test if our randomization schema worked. Since we will stratify our randomization by HS program, we anticipate that an equal number of children will receive the

Date: January 26, 2017

Principal Investigator: [name].

Application Number: NA_00046455

ABC intervention compared to the control. However, if the ICC values indicate a cluster effect, this will be included in our models as nested data models.

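### Head Start program, the randomisation stratum, should be in the models regardless of the observed ICC; a minor, nearly free change that matters mainly for one secondary contrast

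*Combined protocol and SAP*

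**What the plan says.** - **Randomization (section 4, Study Procedures).** Each child is allocated separately, in blocks. On strata: "We will stratify randomization by Head Start program to control for clustering within Head Start programs".
- **Statistical plan (Study Statistics, item c).** ICCs among children from the same program are to be computed "for all outcome variables to test if our randomization schema worked". Program enters the analysis only afterwards: "However, if the ICC values indicate a cluster effect, this will be included in our models as nested data models". No ICC value, test, time point or choice of arms is given for that decision, and the plan does not say whether one decision serves all outcomes. Nowhere else is program included unconditionally. The methods named are "weighted Generalized Estimating Equations or likelihood methods", with no small-sample rule.
- **Objectives (section 2).** The secondary objective asks whether program-level implementation, classed as high or low, "moderates the impact of child-level treatment assignment (ABC vs. Control) on measures of asthma morbidity". Hypothesis 3 then compares ABC children in high-implementation programs "when compared with participants receiving the ABC intervention in low implementation of HS-level asthma education, or Control group participants".
- **Study design (section 4, item a).** On program participation: "we will evaluate over five years the overall HS participation in the HS-level asthma education program". It does not say whether a program is rated once or repeatedly.

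**The concern.** Two things are wrong whatever the numbers.

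1. A stratification factor should be in the analysis because of the design, not because of an estimate made after the data are in. Here the trigger is undefined, so it could be chosen late and differently for each outcome.
2. An outcome ICC measures how alike children in one program are. It carries no information on how they were allocated, so it cannot show whether the randomisation worked.

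The size of the consequence depends on the comparison.

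- **ABC versus control** is made within programs. Leaving program out makes the standard error slightly too large.
- **ABC-high versus ABC-low** is made between programs if each program has one rating. Leaving program out makes the standard error too small.
- **ABC-high versus controls** is partly between and partly within programs.
- **The arm-by-implementation interaction**, which is the moderation question itself, is within programs.

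**Working it through.** **Inputs from the plan.** 16 programs (abstract); 406 enrolled, 15% loss, 346 analysed (statistical plan); SD 6.85 days (power section); 2-3 symptom-free days a month as a meaningful improvement (primary outcome variable). The plan gives no type I error or ICC to reproduce. Its analysed number does reproduce: 406 × 0.85 = 345.1, rounded up to 346.

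**Assumed, because the documents do not give them.** Two-sided alpha 0.05; true ICC 0 / 0.02 / 0.05 / 0.10; 8 high and 8 low programs; one rating per program; arms balanced within program; one time point.

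**Step 1. ABC versus control, program left out.** With arms balanced within program, the true variance is (1 − ICC) times what the model assumes.
- SE ratio 1/√(1 − ICC) at ICC 0.02 / 0.05 / 0.10: 1.010 / 1.026 / 1.054.
- Type I error 2[1 − Φ(1.96/√(1 − ICC))]: 4.8 / 4.4 / 3.9%.
- Power for 2 days at ICC 0.10: model SE = 6.85 × √(2/173) = 0.736; true SE = 0.736 × √0.90 = 0.699. Program included: Φ(2/0.699 − 1.96) = 81.7%. Omitted: Φ[(2 − 1.96 × 0.736)/0.699] = 78.7%. The loss is about 3 points. For 2.5 days it is 1.2 points (94.7 v 93.5%), and for 3 days 0.3 points.

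**Step 2. ABC-high versus ABC-low, program left out.** ABC children per program: m = 346/16/2 = 10.8. Design effect = 1 + (m − 1) × ICC.
- ICC 0.02 / 0.05 / 0.10: design effect 1.20 / 1.49 / 1.98; true SE 1.1 / 1.2 / 1.4 times the model SE.
- Type I error 2[1 − Φ(1.96/√DE)]: 7.3 / 10.8 / 16.4%.

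**Step 3. The same contrast under the conditional rule.** This is a simulation with 20,000 trials per ICC (simulation error about 0.15 points at 5%). When the trigger fires, a program-level t test on 14 df is used; otherwise program is ignored.

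| Trigger | ICC 0 | 0.02 | 0.05 | 0.10 |
|---|---|---|---|---|
| F test, p < 0.05 | 4.7% | 5.9% | 5.7% | 5.3% |
| Estimated ICC ≥ 0.05 | 4.9% | 6.6% | 6.7% | 5.8% |
| Estimated ICC ≥ 0.10 | 5.0% | 7.3% | 10.1% | 9.5% |
| Never included | 5.0% | 7.4% | 11.2% | 16.8% |
| Always, program-level t test | 5.0% | 5.1% | 5.1% | 5.2% |

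At true ICC 0.05 the three triggers bring program in 69%, 45% and 8% of the time, so the undefined trigger largely decides which analysis is run. A 5/11 split gives almost the same figures (at most 10.0% with the 0.10 cut-off).

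**Step 4. The other comparisons and readings.**
- ABC versus control under the rule: 4.8-5.2% with any of the three triggers.
- Arm-by-implementation interaction: 4.5-5.2% under the rule; 4.1-5.1% with program omitted.
- ABC-high versus all controls: 4.8-6.5% under the rule.
- ABC-high versus ABC-low with every program re-rated yearly (four enrolment years assumed): 4.5-6.0% under the rule.

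**Step 5. The form of the adjustment.** Including program does not by itself secure 5% for ABC-high versus ABC-low. A GEE clustered on 16 programs with an uncorrected sandwich SE and a normal reference gives 8.8-9.0% at every ICC. A REML random intercept tested on 14 df errs the other way: 3.3-4.2% for ICC 0.01-0.10. With program fixed effects and one rating per program, the contrast is not estimable (19 design columns, rank 18).

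**The case against.** The plan does not ignore clustering. It stratifies by program for that purpose and promises nested models if clustering appears, so the gap is an undefined trigger. The natural reading of the trigger is a significance test, which keeps the error near 5-6%. The 10% figure needs a high cut-off, a true ICC of 0.05-0.10 and a single rating per program, and it concerns one half of one secondary hypothesis. Mandatory program terms might also be unstable for sparse outcomes such as hospitalisations.

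Most of this stands and sets the weight at minor. It does not defend the rule: the plan names no test, and using the stratum costs almost nothing. The remark on sparse outcomes is a caution, since the documents give no event rates, but the form of adjustment should allow for it.

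A reader might infer three stronger things that the documents do not support.

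- *The primary comparison is at risk of false positives.* It is not: allocation is by child within program, and omission is conservative.
- *Hypothesis 3 as a whole runs at 10% or more.* The moderation test is not inflated, ABC-high versus controls reaches at most 6.5% under the rule, and 11-17% arises only when program is never included and the ICC is 0.05-0.10.
- *The trigger alone drives the error.* The unknown ICC, the number of ratings and the small-sample method matter as much.

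**Conclusion.** The point holds as a minor, nearly free improvement. That the rule is undefined, and that outcome ICCs cannot test a randomisation, follow from the text and need no assumed figure.

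The consequence for ABC versus control is small and conservative. For ABC-high versus ABC-low, type I error under the rule lies between about 5% and 7% for the F-test and 0.05 triggers. It reaches about 10% only with a cut-off near 0.10 together with a true ICC of 0.05-0.10. These figures rest on the assumed alpha, ICC range, 8/8 split and single rating; with yearly re-rating the rule stays at 4.5-6%. They also take the ABC effect to be the same in all programs. If it varied, the ABC-versus-control and interaction tests would be somewhat inflated, and a program intercept would not cure that.

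**What to change.** Replace the conditional sentence with text along these lines:

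- All ABC-versus-control models include Head Start program, the randomisation stratum, regardless of the observed ICC. The form is chosen in advance and must also suit sparse event outcomes.
- Contrasts between high- and low-implementation programs always account for program with a small-sample method. Examples are a program-level t test (about 14 df with one rating per program, close to 5%), a random intercept with small-sample df (somewhat conservative at low ICC), or a small-sample-corrected sandwich SE if GEE is used. Program fixed effects are not used for this contrast if each program has one rating.
- The arm-by-implementation interaction is estimated with a program intercept, and with a program-by-arm random effect as a sensitivity analysis.
- The plan states whether programs are rated once or repeatedly.
- ICCs are reported descriptively. The statement that they test the randomisation is deleted, and allocation by program is checked from the allocation log.

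Cost: wording only, with no new data or participants. ABC versus control gives up at most 15 of about 346 degrees of freedom. Intervals for high versus low implementation become wider than a model without program would show, which is the true precision available from 16 programs.

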All participants who enroll in the trial and are randomized to the control condition will receive (along with all other Head Start students) Head Start-based asthma educational activities and materials. CC participants will be contacted for follow-up assessment at 3, 6, 9, and 12 months.

Intervention Condition (IC).

Participants randomized to the intervention condition will also receive the HS-level asthma education program activities and materials. In addition, participants will receive a culturally-specific home-based asthma education intervention, specifically designed to reflect known cultural barriers to effective asthma management among low-income minority families. Over the course of the intervention the family will receive four weekly home visits (30-45 minutes each; approximately 1-, 2-, 3-, and 4- weeks postrandomization) and three quarterly phone sessions (20-30 minutes each, after the completion of each follow-up assessment) by a trained asthma educator. The asthma educator has the knowledge, comfort and experience with the community. The asthma educator overarching goals for intervention are to address known cultural barriers including underutilization of asthma primary care, overestimation of asthma control, perceptions that asthma is an episodic illness that only needs acute treatment, negative beliefs about controller medications, and environmental risk factors in the home. The intervention will begin by

Date: January 26, 2017

Principal Investigator: [name].

Application Number: NA_00046455

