In order to enhance the efficacy, reach, integration and sustainability of the proposed home-based asthma education intervention, we will train and facilitate Head Start staff to implement and deliver the HS-level asthma education program, utilizing existing community resources whenever possible. The HS-level asthma education program will consist of the following four components: 1) bi-annual Staff Training Workshops (for which HS staff will receive continuing education credit), 2) provision of relevant asthma educational materials drawn from public resources, 3) identification and facilitation of community resources relevant for achieving goals, and 4) ongoing expert facilitation of Head Start initiated asthma education activities (e.g. parent workshops, health fairs, newsletters)

- a. Study duration and number of study visits required of research participants. The study duration is 12 months for each participant. All participants will complete 5 surveys. The intervention condition will also receive 3 home visits and 4 phone calls. Head Start staff will be offered the opportunity to attend asthma education workshops which contain 8 modules and a postevaluation two times a year.
- b. Blinding, including justification for blinding or not blinding the trial, if applicable. N/A
- c. Justification of why participants will not receive routine care or will have current therapy stopped.

All subjects will receive an asthma educational program within the Head Start setting which is not currently provided. Participants in the intervention condition will receive additional intervention.

- d. Justification for inclusion of a placebo or non-treatment group.
Both groups will receive a Head Start level educational intervention, thus there is no nontreatment group. The intervention group will receive additional intervention sessions.
- e. Definition of treatment failure or participant removal criteria.
Any participant can leave the study at any time. Participants will be removed from the study prior to randomization if the baseline assessment is not complete. Treatment failure is defined as subjects not completing the home visits. After the participant is randomized, subjects will not be removed from the study by investigators.
- f. Description of what happens to participants receiving therapy when study ends or if a participant's participation in the study ends prematurely.

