[name] at University of Maryland-Baltimore County will be completing secondary data analysis. UMBC has requested that Johns Hopkins Medicine IRB serve as the site's IRB. De-identified data sets will be sent by Johns Hopkins via HIPAA and JHMI compliant protocols and study participants will not directly interact with UMBC.

d. Early stopping rules.

The DSMB will develop early stopping rules based on their review of the study protocol. Once these rules have been developed they will be shared with the IRB.

7. Risks

- a. Medical risks, listing all procedures, their major and minor risks and expected frequency. Parents may be uncomfortable discussing the child's asthma. Some families may experience possible family discord if the asthma management practices change. Asthma educators will be trained to interact with families in a positive, non-judgmental manner that encourages honest communication and a partnership approach to asthma education. Care will be taken to help family members discover ways that they can all work together to better manage the child's asthma.

Maryland law requires us to tell the local or state authorities if we suspect abuse or neglect of a child or dependent adult. If anyone reports that they plan to harm someone, we are required to contact the police. We may also warn the person who is at risk. The caregiver will be informed of the limits of confidentiality during the informed consent process and reminded of this during the first home visit. There are no risks to HS staff completing the staff survey.

b. Steps taken to minimize the risks.

Asthma educators are trained to learn how to clinically address family conflict about asthma practices. The family may refuse to allow the home visits at any time. If this were to happen, the child would continue to be followed and we will categorize him/her as receiving low dose intervention.

c. Plan for reporting unanticipated problems or study deviations.

In the event that any adverse event occurs during the course of the study, the adverse event will be reported to the Johns Hopkins University School of Medicine IRB using the IRB's Protocol Event Report by PI Form with supporting documentation of the adverse event and will also be reported to the study DSMB.

d. Legal risks such as the risks that would be associated with breach of confidentiality.

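### Adverse events are reported only as they surface, and ABC families have 11 scheduled contacts after randomisation against 4 in Control, so unsolicited harms could appear more often in ABC at equal true rates

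*Combined protocol and SAP*

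**What the plan says.** Section 7 (Risks), item c, holds the whole adverse-event plan: "In the event that any adverse event occurs during the course of the study, the adverse event will be reported" to the IRB, and it "will also be reported to the study DSMB". No definition, scripted question, schedule or look-back period is given there or elsewhere.

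Section 7, item a, names two risks: that parents may be uncomfortable talking about the child's asthma, and that "Some families may experience possible family discord if the asthma management practices change". The mitigation given is the training of the asthma educators.

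Contact differs by arm. Under Control Condition, "CC participants will be contacted for follow-up assessment at 3, 6, 9, and 12 months". Under Intervention Condition, "the family will receive four weekly home visits" and "three quarterly phone sessions (20-30 minutes each, after the completion of each follow-up assessment"). The study-duration item of Section 4 gives another mix: "The intervention condition will also receive 3 home visits and 4 phone calls". These two passages contradict each other and must be reconciled, but each adds up to seven.

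Section 4 (Study design) schedules outcome collection at 3, 6, 9 and 12 months. The outcomes include ED visits, hospitalizations, oral steroid bursts, asthma control and caregiver quality of life. Under Health Outcome data, utilization is checked against payer records where these can be had.

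**The concern.** When nobody is scheduled to ask, an event enters the record only if a family happens to mention it to study staff. ABC families have more occasions to do so, and the content of those occasions makes it likelier. Educators discuss caregivers' barriers to asthma care, are trained to encourage openness, and record psychosocial concerns in the ABC Report. No Control counterpart is described.

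At stake is how any difference in event counts between the arms is read, by the DSMB during the trial or in the final report. An excess in ABC could reflect the home visits themselves or only the extra listening. The trial would also be poorly placed to say whether home visits cause more family conflict or distress than Head Start education alone, although the protocol itself lists such conflict and discomfort as risks. The primary outcome and its analysis are untouched.

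**Working it through.** **1. Contacts (from the documents).**
- Control after randomisation: 4 surveys.
- Extra ABC contacts: 4 home visits + 3 phone sessions = 7 (Intervention Condition), or 3 + 4 = 7 (study-duration item).
- ABC after randomisation: 4 + 7 = 11. Ratio 11/4 = 2.75.
- Counting the baseline visit: 12 against 5, ratio 2.4.

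**2. From contacts to reported events (assumptions, not in the documents).** True event rates are equal in the two arms, and event times are uniform over 365 days. Each contact within W days after an event surfaces it with probability p, so an event followed by k such contacts is reported with probability 1 − (1 − p)^k, averaged over event times. Control contacts are placed at days 91, 182, 273 and 365. ABC adds days 7, 14, 21, 28, 98, 189 and 280, which uses the 4 + 3 mix; the documents do not settle the mix.

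With W = 100 days:

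| p | ABC | Control | Ratio |
|---|---|---|---|
| 0.2 | 0.358 | 0.211 | 1.69 |
| 0.3 | 0.499 | 0.315 | 1.58 |
| 0.5 | 0.721 | 0.518 | 1.39 |
| 0.7 | 0.874 | 0.715 | 1.22 |

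Over the same p, the ratio runs from about 2.1 down to 1.65 with a 30-day window, and from 1.34 down to 1.03 with an unlimited one. The full range is about 1.0 to 2.1. Every case gives an excess in ABC, but the excess nearly vanishes when p is high and the window long.

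**3. A harm present throughout follow-up.** Here k is simply 4 or 11. At p = 0.2: 1 − 0.8^4 = 0.590 against 1 − 0.8^11 = 0.914, ratio 1.55. At p = 0.5: 0.938 against about 1.00, ratio 1.07. At p = 0.05: 0.185 against 0.431, ratio 2.3. Rarer mention gives a larger ratio, up to the limit of 2.75.

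**4. What a nominal comparison would show.** No such test is planned; this only gives scale. Take 203 per arm (Study Statistics, item c), no dropout, p = 0.3 and W = 100 days. Expected reports are 203 × true proportion × detection probability. At 10%, for example, 203 × 0.10 × 0.499 = 10.1 in ABC and 203 × 0.10 × 0.315 = 6.4 in Control.

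| Assumed true proportion | ABC children | Control children | Chance of a significant ABC excess (two-sided 5%) |
|---|---|---|---|
| 5% | 5 | 3 | about 8% |
| 10% | 10 | 6 | about 15% |
| 20% | 20 | 13 | about 27% |
| 40% | 41 | 26 | about 52% |

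With equal ascertainment, the nominal chance in that direction is 2.5%. At p = 0.7 and a 10% proportion it is about 8%.

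**5. Under the fix.** If only answers to a common survey question are compared, scheduled opportunities are 4 against 4, ratio 1.0.

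**The case against.** The strongest reply is that the serious asthma harms are already elicited evenly. ED visits, hospitalizations, steroid bursts, asthma control and quality of life are collected on one schedule in both arms, with payer data as a check on utilization when available. This stands, and it confines the point to unsolicited, mainly psychosocial events.

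Three stronger readings are tempting, and the documents support none of them.

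- *Control families are never asked about discord or discomfort.* The survey content is not given, and nothing says that ABC families are asked either. What can be said is that no elicitation is described in either arm. Discomfort in talking about asthma could also arise from the surveys that both arms complete.
- *ABC will show more adverse events.* Size and direction depend on unstated quantities. Educators might under-report events linked to their own visits, and effective education could lower true asthma events.
- *The DSMB will be misled, with a false signal about half the time.* That figure needs a 40% event proportion, which is hard to assume for unsolicited events in an education trial. No between-arm test of adverse events is planned, stopping rules are left to the DSMB, and nothing prevents the DSMB from asking how an event came to light.

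It can also be said that item c answers a form field on reporting unanticipated problems and was never meant as a harms analysis. That is fair. But it is the only adverse-event text in the plan, and it leaves unequal ascertainment unaddressed.

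**Conclusion.** The concern holds in limited form. Event-triggered reporting with 11 against 4 contacts gives unsolicited events unequal chances to surface, and the more plausible direction is more reports in ABC. The contact counts are firm under either description of the visit mix. The size is not: a ratio of about 1.0 to 2.1, and an 8% to 52% chance of a nominal ABC excess at p = 0.3, rest on assumed detection, look-back window and event rate, with equal true rates and equal per-contact detection in the two arms. Survey-collected asthma events are outside the problem. This is a gap in harms ascertainment that is cheap to close, and it does not bear on the primary result.

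**What to change.** In Section 7, item c:

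1. State that the same scripted harms question is asked in both arms at the 3-, 6-, 9- and 12-month surveys, with one item on family conflict over asthma care and one on distress from taking part.
2. State that any between-arm harms summary, for the DSMB or the final report, uses these survey-elicited events plus the ED visits and hospitalizations collected by survey.
3. Keep individual reporting of every event first heard by an educator, listed separately by source and not compared between arms.

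Separately, reconcile the Intervention Condition text with the study-duration item on the numbers of home visits and phone contacts.

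Cost: a protocol and survey amendment and about a minute more per survey, with no added staff, visits or participants. The downside is that comparative tables would omit events known only to educators, though these are still reported and listed.
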